### **PRIOR TREATMENT APPROACHES**

Recording of any and all prior treatments that the subject has tried to manage his or her onychomycosis of the target toenail, including:

- (i) Over-the-counter (OTC) medications and treatments (oral and topical)
- (ii) Prescription medications and treatments (oral and topical)
- (iii) Herbal supplements (oral and topical)
- (iv) Traditional therapies (e.g. surgery, YAG laser therapy)
- (v) Alternative therapies (e.g. acupuncture)

Noting, for each medication/treatment/therapy tried:

- (i) Date(s) of use/application
- (ii) Duration of use/application
- (iii) Perceived effectiveness

### **CONCOMITANT MEDICATIONS**

Recording of any and all current medications that the subject is taking for any reason, including:

- (i) Over-the-counter (OTC) medications and treatments
- (ii) Prescription medications and treatments
- (iii) Herbal supplements

Noting, for each medication:

- (i) Indication for use
- (ii) Dosage and frequency of use
- (iii) Duration of use

### **SUBJECT DEMOGRAPHICS**

- (i) Gender
- (ii) Age
- (iii) Ethnicity

## **CLINICAL AND OUTCOME EVALUATION TOOLS**

### **MYCOLOGICAL EVALUATION: BIOMED INTRAY™ DM CULTURE**

The BioMed InTray™ DM Culture will be used to determine the presence or absence of fungal organisms and to identify the type of dermatophyte in the case of a positive fungal determination.

The BioMed InTray™ DM Culture device allows for simultaneous detection and observation of the dermatophyte fungal group, including detection of dermatophytes of *Microsporum*, *Epidermophyton* and *Trichophyton (T. rubrum)*, as well as *C.albicans*.

The InTray™ DM Culture testing will be performed from the same target toenail for each subject at each administration. For cultures positive for the presence of fungal organisms, the type of dermatophyte identified will also be recorded.

### **PHOTOGRAPHIC DOCUMENTATION**

A photograph of the study great toenail will be taken with the great toe placed in a horizontal-vertical *mm scale measurement recording device*. This device is designed to maintain the great toenail in the same position at each photographic time point to ensure consistency of measurements across all evaluation time points and all toenails, and to provide a mm reference scale in the event that measurement of mm of clear nail is necessitated.

An image of the mm scale recording device and its application is shown below in Figure 8.

[figure not shown]

Figure 8: Positioning of the great toenail in the mm scale recording device

The photograph of the study great toenail will be taken using a high resolution digital camera, following a standardized methodology, ensuring consistency of equipment, lighting, distance, resolution, etc. between and across all subjects, test sites and measurement time points

## MM OF CLEAR NAIL MEASUREMENT TOOL: THE GNU IMAGE MANIPULATION PROGRAM (GIMP 2.8)

The GNU Image Manipulation Program (GIMP 2.8) will be employed in this study for the measurement of the linear millimeters (mm) of clear nail bed.

The GNU Image Manipulation Program (GIMP 2.8) was originally released in January 1996 as the *General Image Manipulation Program*, having been created by Spencer Kimball and Peter Mattis as the result of a college project at the University of California, Berkeley. In 1997, the definition of the acronym 'GIMP' was changed to mean the *GNU Image Manipulation Program*, by permission of Richard Stallman, to also reflect its existence under the *GNU Project*.

The GNU Image Manipulation Program (GIMP 2.8) is a multi-platform image/photo manipulation software. It is a raster editor, such that it performs operations directly on the pixels that make up the image and not a vector editor.

GIMP is suitable for a variety of image manipulation and analysis tasks, including photo retouching, image composition, and image construction. It has many capabilities. It can be used as a simple paint program, an expert quality photo retouching program, an online batch processing system, a mass production image renderer, an image format converter, etc. It is designed to be augmented with plug-ins and extensions to do just about anything. The advanced scripting interface allows everything from the simplest task to the most complex image-manipulation procedures to be easily scripted.

Complete details of GIMP, its specifications, operations and applications can be found on the website: [www.gimp.org](http://www.gimp.org).

Erchonia Corporation conducted a validation study of the GIMP 2.8 software to validate both the method/tool and the measurement methodology for the specific application of the measurement of linear mm of clear nail prior to the initial LunulaLaser™ trial. The results of the validation study have been reviewed and accepted by the FDA as a validated means of measuring linear mm of clear nail in onychomycosis-infected toenails.

In this study, GIMP 2.8 will be used to measure the linear mm of clear nail of the onychomycosis infected great toenail from the digital toenail images captured, defined as the distance from the proximal nail fold to the most proximal area of nail dystrophy. A straight line will be created between the two points, and the GIMP 2.8 system software will formulate a measurement of that line. An example is shown in Figure 9 to the right, demonstrating how total nail length and linear measurement of mm of clear nail from the proximal nail fold to the most proximal area of nail dystrophy is determined.

[figure not shown]

Figure 9: Application of the GIMP 2.8 to measurement of mm clear nail length

The 'GIMP 2.8 Software Measurement Methodology Instruction Sheet' contained in **Appendix A** details the instructions for operation and application of the GIMP 2.8 software system for measurement of linear mm clear nail measured from the proximal nail fold to the most proximal dystrophic component that will be followed by the study investigators.

## **NAIL ETCHING**

A shallow etched horizontal line will be placed in the target study toenail, at the proximal-most area of dystrophy and aligned parallel to the horizontal portion of the proximal nail fold. This line will serve as both a marker for measuring nail growth rate as well as distance from the proximal nail fold to the most proximal point of the nail dystrophy.

## **PERCENTAGE OF CLINICAL ONYCHOMYCOSIS INVOLVEMENT DETERMINATION**

Visual estimation of the % of clinical onychomycosis disease involvement in the target great toenail will be determined by the investigator based upon his or her professional and clinical knowledge and experience.

## **SUBJECT DAILY DIARY**

On each day of the study, the subject will record the following measures in a Daily Diary supplied by the investigator at the test site on the day of the first treatment administration.

- ✓ Compliance with abstinence from other (non-study) treatments for toenail fungus
- ✓ Compliance with abstinence from the use of nail cosmetics on study toes
- ✓ Any changes in medication use and/or therapies engaged in from those reported at baseline evaluation
- ✓ Potential perceived adverse events, as described in the 'Adverse Events' evaluation tool listed below.
- ✓ Any study-related comments, if and as desired

## **ADVERSE EVENTS EVALUATION**

Prior clinical trials applying the Erchonia® LunulaLaser™ to toenail onychomycosis have not yielded any adverse events or reactions. Numerous additional clinical trials applying Erchonia® low level laser for various different indications have also not yielded any adverse events or reactions. Therefore, it is unlikely and not expected that any adverse events will result from implementation of this clinical study protocol.

However, potential adverse events that may feasibly occur from application of the Erchonia LunulaLaser™ include, but are not necessarily limited to: skin irritation, discoloring, rash, indentations and re-infection.

Adverse events evaluation will include formal evaluation of the treatment area and surrounding skin area by the investigator at each subject test site visit as well as review of any potential events reported or recorded in the Subject Daily Diary by the subject. Adverse events evaluation will be conducted for all toenails on the foot with the study treated toenail.

Any and all observation(s)/report(s) of potential adverse events, whether observed by the investigator or reported by the subject, whether anticipated or unanticipated, will be recorded on the Adverse Events case report form and subsequently evaluated by the investigator for its relation to the study procedure and whether or not any corrective action needs to be taken. All potential adverse events recorded will be appropriately reported to the governing IRB, as applicable.

## **STUDY PROCEDURE PROTOCOL**

### **PRE-TREATMENT ACTIVITIES**

#### **STUDY QUALIFICATION EVALUATION: PROGRESSIVE EVENTS**

##### **SIGNING OF INFORMED CONSENT FORM**

The PI commences by presenting and reviewing in detail the items in the informed consent form with the individual and answering any questions he or she may have. To proceed, the individual must willingly sign the informed consent form.

##### **ASSIGNMENT OF SUBJECT IDENTIFICATION NUMBER**

The subject is assigned a unique subject identification number based upon his or her order of entry into the study. Additional information about the informed consent and subject ID number assignment is contained in a later section of the protocol titled, "SAFETY AND CONFIDENTIALITY ISSUES."

#### **INCLUSION/EXCLUSION CRITERIA**

##### ***MYCOLOGICAL CRITERIA EVALUATION***

The BioMed InTray™ DM culture will be performed on the intended study great toenail:

*Inclusion Criteria:* The subject will continue to the Clinical Criteria Evaluation phase if the results of the InTray™ DM culture results satisfy both of the following inclusion criteria:

- Detection of the presence of fungal infection
- Identification of *Trichophyton rubrum* (*T. rubrum*) or other common dermatophyte

*Exclusion Criteria:* The subject's participation in the study will end at this time if the results of the InTray™ DM culture satisfies either or both of the following exclusion criteria:

- Lack of detection of the presence of fungal infection
- Identification of a fungal species other than *Trichophyton rubrum* (*T. rubrum*) or other common dermatophyte, such as *C. albicans* or mixed dermatophyte/*Candida* infection or non-fungal organisms such as mold or bacteria

##### ***CLINICAL CRITERIA EVALUATION***

*Inclusion Criteria:* The subject will continue to the Baseline Assessment phase if all of the following clinical inclusion criteria are satisfied:

- Visual clinical presentation of onychomycosis in the target great toenail is distal subungual onychomycosis (DSO), visualized as a nail with normal surface texture and thickness but variable "bays" of white nail that extend from the distal nail tip proximally into the area of the nail bed
- Clinical involvement of onychomycosis in the target toenail is between 20%–50%
- Subject is willing and able to refrain from employing other (non-study) treatments (traditional or alternative) for his or her toenail onychomycosis throughout study participation.
- Subject is willing and able to refrain from the use of nail cosmetics such as clear and/or colored nail lacquers throughout study participation
- Male or female
- 18 years of age or older

**Exclusion Criteria:** The subject's participation in the study will end at this time if any one or more of the following clinical exclusion criteria are satisfied:

- Visual clinical presentations of onychomycosis in the target great toenail that are inconsistent with the clinical presentation of distal subungual onychomycosis (DSO), in whole or in part (i.e. indicative of mixed etiology); specifically visual clinical presentations consistent with one or more of the following:
  - *Proximal subungual onychomycosis (PSO):* visualized as a white discoloration below the nail plate at the base of the nail, near the lunula. The distal nail retains normal appearance and texture. PSO involves infection near the matrix, deep to the nail. It may be associated with trauma to the nail or to immune compromise
  - *Superficial white onychomycosis (SWO):* visualized by the appearance of a white coating on the nail surface that can be eliminated by filing or buffing the surface of the affected portion of the nail
  - *Complete dystrophy:* Nails which are 100% dystrophic are manifested by yellowing and thickening of the entire nail unit
  - *Other nail changes:* Nails that visually present with changes that appear as parallel lines, small pinpoint depressions, brown spots, black or brown linear streaks, complete yellowing of all nails without textural change, green debris below the nail, or notches in the nail margin
- Less than 2mm clear (unaffected) nail plate length beyond the proximal fold
- Presence of dermatophytoma (thick masses of fungal hyphae and necrotic keratin between the nail plate and nail bed)
- Infection involving lunula e.g., genetic nail disorders, primentary disorders
- Severe plantar (moccasin) tinea pedis
- Psoriasis of the skin and/or nails, lichen planus, or other medical conditions known to induce nail changes
- Onychogryphosis
- Trauma from ill-fitting shoes, running, or overly-aggressive nail care
- Previous toenail surgery
- Uncontrolled diabetes mellitus
- Peripheral vascular disease
- Recurrent cellulitis
- Lymphatic insufficiency
- Immune compromise (whether due to underlying medical disorders or immunosuppressive treatments)
- Other compromised states of health
- Known photosensitivity disorder
- Use of oral antifungal drugs in the prior 6 months
- Use of topical treatment of the skin or nails within the prior 2 months
- Any abnormality of the toenail that could prevent a normal appearing nail from occurring if clearing of infection is achieved.
- Current trauma, open wound on or about the treatment area
- Deformity of the target toe/toenail secondary to fungal infection/onychomycosis due to prior injury, surgical procedures or another medical condition
- Pregnant or planning pregnancy prior to the end of study participation
- Serious mental health illness such as dementia or schizophrenia; psychiatric hospitalization in the past two years

- Developmental disability or cognitive impairment that would preclude adequate comprehension of the informed consent form and/or ability to follow study subject requirements and/or record the necessary study measurements
- Involvement in litigation and/or receiving disability benefits related in any way to the parameters of the study
- Participation in a clinical study or other type of research in the past 30 days.

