## **STUDY RATIONALE AND JUSTIFICATION: LOW LEVEL LASER THERAPY AS A TREATMENT FOR TOENAIL ONYCHOMYCOSIS**

Presently, there is no perfect cure for toenail fungus. Even the most effective oral medications are successful only about half of the time. Topical medications are successful less than 10% of the time. As 10% of the adult population is affected by toenail onychomycosis, the need for a more effective and lasting cure is evident.

Recently, application of low level laser therapy to the affected toenail over a four-week period using the Erchonia® LunulaLaser™ device has been clinically demonstrated to effect increase in clear nail in onychomycosis-infected toenails, and the device subsequently received FDA clearance to be marketed for this indication (K153164) based on this clinical outcome.

Unlike medication-driven treatments for toenail fungus which can have many side effects including serious ones such as liver toxicity, low level laser therapy presents minimal risk of side effects. Laser therapy is applied to toenail onychomycosis by shining a laser light through the toenail. The laser light vaporizes the fungus while leaving the skin and surrounding tissue unharmed, in a simple, quick, non-invasive and pain-free manner.

The goal of this current study is to expand the present indication for use for the Erchonia® LunulaLaser™ of: “The LunulaLaser™ device is indicated for use for the temporary increase of clear nail in patients with onychomycosis (e.g. dermatophytes *Trichophyton rubrum* and *T. mentagrophytes*, and/or yeasts *Candida albicans*, etc.)” (K153164) from the aesthetic claim of changing the nail appearance to the medical claim of eradicating the underlying fungal infection. As such, this clinical study protocol design is intended to provide data to support an indication for use of ‘treatment of onychomycosis’ through application of the Erchonia® LunulaLaser™.

Prior clinical trials evaluating application of the Erchonia® LunulaLaser™ to toenail onychomycosis have reported negative culture results at completion of treatment administration, providing support and justification for conducting a controlled clinical trial to specifically assess and support a claim of treatment of onychomycosis for the Erchonia® LunulaLaser™ device.

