## STUDY RESULTS

**Primary Outcome Measure: Change in mm of Clear Nail from Baseline to Study Endpoint:** The primary efficacy outcome measure in this study was the mm of clear nail growth at 6 months post procedure administration end relative to Baseline (pre-procedure administration). Individual toenail success was defined as 3 mm or more of clear nail growth at 6 months post-

procedure end relative to baseline. Overall study success was defined as an anticipated 60% of treated toenails meeting the individual toenail success criteria.

Sixty seven per cent (67%) of all study treated toenails evaluated in this study met the study individual toenail success criteria, exceeding the pre-established overall study success goal of 60% by 7%. The magnitude of the mean change in mm of clear nail from baseline to 6 months post-procedure for all treated toenails was an increase of 5.18 mm, 2.18 mm in excess of the pre-established 3 mm increase success criteria. A t-test for paired samples found this mean change of +5.18 mm in clear nail to be statistically significant ( $t=-8.0$ ;  $df=53$ ;  $p<0.0001$ ).

**ADVERSE EVENTS:** No adverse event was reported or observed for any subject throughout any of the three clinical trials from which this study's retrospective sample was drawn.

**CONCLUSION:** The Erchonia LunulaLaser™ is an effective tool for increasing clear nail in toenails infected with onychomycosis, significantly increasing mm of clear nail over a 6 month period following completion of the 4-week procedure administration phase.

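### Eligibility has no exclusion or washout for prior laser or light treatment of the target nail, including the marketed LunulaLaser, and no planned analysis separates such subjects

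*Combined protocol and SAP*

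**What the plan says.** The exclusion list under Clinical Criteria Evaluation has two treatment washouts: "Use of oral antifungal drugs in the prior 6 months" and "Use of topical treatment of the skin or nails within the prior 2 months". It also excludes "Previous toenail surgery", with no time limit, and "Participation in a clinical study or other type of research in the past 30 days". None of the mycological or clinical criteria names laser, light or photodynamic treatment.

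Under Prior Treatment Approaches, the baseline history lists "Traditional therapies (e.g. surgery, YAG laser therapy" as a category separate from oral and topical products. Dates, duration and perceived effectiveness are recorded for each treatment. No eligibility consequence follows.

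The only general restriction on other treatments looks forward: "Subject is willing and able to refrain from employing other (non-study) treatments (traditional or alternative) for his or her toenail onychomycosis throughout study participation". General Assessment Conditions repeats it for the course of participation.

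The Study Rationale states that "the device subsequently received FDA clearance to be marketed for this indication (K153164"), and Device Description and Specifications says the study device is identical to the cleared one. Under Study Treatment Group the trial is single-arm. Subgroup and Covariate Analyses lists site, baseline involvement, organism, side, duration of disease and demographics, but not prior treatment.

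**The concern.** Clinical Cure rests on clear-nail gain, or complete clearance, 12 months after the first treatment, and Day 1 is the baseline. On the sponsor's own account a laser course keeps acting after it ends: the retrospective study concludes that the device works by "significantly increasing mm of clear nail over a 6 month period following completion of the 4-week procedure administration phase". A nail treated shortly before enrolment could still be gaining clear length when the study baseline is taken. With no concurrent control, nothing in the design separates that gain from the effect of the study's own treatments.

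The problem can also run the other way. Patients who had laser treatment and still have infected nails may be a group selected for poor response. In either case these subjects receive more total laser exposure than the regimen under Treatment Administration Protocol, and the cure rate no longer describes that regimen alone.

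**Working it through.** **1. Which earlier treatments have an entry rule?**

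| Earlier treatment | Entry rule |
|---|---|
| Oral antifungal drugs | 6 months |
| Topical treatment of skin or nails | 2 months |
| Toenail surgery | excluded at any time |
| Any research participation | 30 days |
| Laser, light-based or photodynamic treatment | none |

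Could another row cover laser? The topical rule does not, because Prior Treatment Approaches lists laser apart from topical products; even if stretched, it would reach back only 2 months. The research rule does not reach commercial treatment. Surgery and YAG laser share one line of the history form, yet only surgery has an exclusion.

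**2. How much gain could carry over?** The retrospective study reports a mean of +5.18 mm, from the pre-procedure baseline to 6 months after a course of four weekly treatments. Against the 12 mm criterion that is 5.18/12 = 43%. It is a ceiling on average carry-over within that interval, for two reasons:

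- It is uncontrolled, so it includes growth that would have occurred anyway.
- It starts before the course. Growth that precedes the study's Day 1 cannot be miscredited.

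Example: a course finished 5 weeks before Day 1, with gain assumed linear. The interval is about 3 + 26 = 29 weeks, of which 3 + 5 = 8 have passed. The remainder is 5.18 × 21/29 = 3.75 mm, or 3.75/12 = 31% of the criterion.

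**3. What is one subject worth?** The plan's 66 reproduces as 60/(1 − 1/12) = 65.45, rounded up. The 70% clinical criterion needs 0.70 × 66 = 46.2, so 47 responders. One subject is 1/66 = 1.5 points.

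**4. Illustration.** The documents give neither the share of prior-laser patients nor their response. Assume that 5%-10% of 66 subjects are affected (3.3 to 6.6, taken as 3 or 7) and that the regimen's true rate is 60% in the others.

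- Expected rate if all affected subjects respond: (3 + 0.60 × 63)/66 = 61.8%, or (7 + 0.60 × 59)/66 = 64.2%.
- Expected rate if none responds: (0.60 × 63)/66 = 57.3%, or (0.60 × 59)/66 = 53.6%.

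The chance of 47 or more responders is the exact binomial tail of Bin(66 − k, 0.60) + Bin(k, q), with k affected subjects who respond at rate q:

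| Affected subjects k | q = 67% | q = 100% |
|---|---|---|
| 0 | 4.0% | 4.0% |
| 3 | 4.4% | 7.0% |
| 7 | 5.1% | 13.7% |

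The 67% is borrowed from the retrospective study, where success meant a gain of 3 mm or more, so it is only a reference value. The effect runs from negligible to material, depending on inputs the documents do not supply.

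**The case against.** The strongest defence is that other criteria already filter these patients. A culture-negative nail is excluded. The sponsor's earlier mycology study, summarised under Supporting Materials, found every treated nail culture-negative two weeks after baseline. Entrants also need 20%-50% involvement and may not have less than 2 mm of clear nail. On those figures, a recent LunulaLaser patient who is still culture-positive is a mycological failure of the device, and the mean gain of all treated nails need not apply to that patient. This stands as a limit on the size of the problem. It does not close the gap: the filter misses persistent positives, relapses and patients treated with other lasers.

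Second, the endpoint asks for more than early growth. Response must be progressive at two sequential timepoints at least 3 months apart, and at least 80% of clinical responders must be culture-negative. One earlier course need not satisfy all of this. That too stands.

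Third, the history form is a catch-all that also lists acupuncture, and the Recruitment text does not say that sites offer laser treatment. The documents therefore do not show that any such patient would enrol. This is also right; the point is that nothing prevents it.

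A reader might go further and infer that one earlier course could supply most or all of the required clearance. On an assumed 20 mm nail with full-width involvement, 20%-50% is 4-10 mm, and 5.18 mm would be 52%-130% of it. The documents do not support that. Nail length is not given, and the 5.18 mm is uncontrolled and counts gain made before Day 1. The 3.75 mm of the five-week example would be 38%-94%, still under the assumed nail length and linear gain.

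**Conclusion.** The omission is real and worth correcting. The criteria contain no rule for prior laser, light-based or photodynamic treatment of the target nail, the device under test is on the market, and the design has neither a control arm nor a planned analysis to separate such subjects.

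The size and direction of the bias cannot be established from the documents. The firm figures are 47 of 66 responders for the 70% criterion and 1.5 points per misattributed subject. Any total, such as 3-7 subjects or 4.5-10.6 points, rests on an assumed 5%-10% prevalence. It also requires every such subject to be a responder only because of the earlier course.

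Two stronger conclusions are tempting and should not be drawn: that the gap certainly inflates the cure rate, and that it favours the device. Carry-over would raise the rate and earlier laser failures could lower it, and the documents do not show which would dominate.

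**What to change.** Add to the exclusion list under Clinical Criteria Evaluation: laser, light-based or photodynamic treatment of the target toenail, including the LunulaLaser, within a stated window. Six months is one example; it matches the oral antifungal window and the sponsor's follow-up after a laser course. That follow-up shows only how long nails were observed, not that the effect ends there, so the sponsor should justify the length chosen.

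Add to the SAP a sensitivity analysis of the primary outcome that omits subjects with any prior laser treatment of the target nail, identified from the Prior Treatment Approaches data. This is preferable to a covariate, which would be informed by very few subjects.

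The cost is a few more screen failures. No new visit, test or data item is needed, and the planned enrolment stays at 66.
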